5.3.4.1 Recommended Dose Modifications

Worst Toxicity CTCAE v4.0 Grade (unless otherwise specified)	Recommended Dose Modifications to cisplatin any time during a cycle of therapy	Recommended Dose Modifications to carboplatin any time during a cycle of therapy
BLOOD AND LYMPHATIC SYSTEM DISORDER		
Anemia		
Grade 1 (Hgb < LLN-10.0 g/dL)	Maintain dose level.	Maintain dose level.
Grade 2 (Hgb < 10.0 g/dL - 8.0 g/dL)	Maintain dose level.	Maintain dose level.
Grade 3 (Hgb < 8.0 g/dL); transfusion indicated	Maintain dose level.	Maintain dose level.
Grade 4 (Life threatening consequences; urgent intervention indicated); related to study drugs	Discontinue study treatment.	Discontinue study treatment.
ANC decreased (Neutropenia)		
Grade 1 (ANC < LLN - 1.5 x 10 ⁹ /L)	Maintain dose level.	Maintain dose level
Grade 2 (ANC < 1.5 - 1.0 x 10 ⁹ /L)	Maintain dose level.	Maintain dose level
Grade 3 (ANC < 1.0 - 0.5 x 10 ⁹ /L)	Omit dose of cisplatin until resolved to CTCAE Grade ≤ 1, and no fever. Then: - If resolved in ≤ 7 days, then maintain dose level - If resolved in > 7 days, then maintain dose level and consider prophylactic growth factor support per ASCO guidelines - If second occurrence, then ↓ 1 dose level for subsequent cycles.	Omit dose of carboplatin until resolved to CTCAE Grade ≤ 1, and no fever. Then: - If resolved in ≤ 7 days, then maintain dose level - If resolved in > 7 days, then maintain dose level and initiate prophylactic growth factor support per ASCO guidelines - If second occurrence, then ↓ 1 dose level for subsequent cycles.
Grade 4 (ANC < 0.5 x 10 ⁹ /L)	Omit dose of cisplatin until resolved to CTCAE ≤ Grade 1, then ↓ 1 dose level; additionally, consider prophylactic growth factor support per ASCO guidelines.	Omit dose of carboplatin until resolved to CTCAE ≤ Grade 1, then ↓ 1 dose level; additionally, consider prophylactic growth factor support per ASCO guidelines.
Febrile neutropenia		
Grade 3 (ANC < 1.0 x 10 ⁹ /L, single temperature of > 38.3°C or a sustained temperature of ≥ 38.0°C)	Omit dose of cisplatin, then - If resolved by ≤ 7 days, then ↓ 1 dose level and consider prophylactic growth factor support per ASCO guidelines. - If not resolved within 7 days despite appropriate management including full clinically indicated course of antibiotics, if indicated, discontinue patient from study treatment.	Omit dose of carboplatin, then - If resolved by ≤ 7 days, then ↓ 1 dose level and consider prophylactic growth factor support per ASCO guidelines. - If not resolved within 7 days despite appropriate management including full clinically indicated course of antibiotics, if indicated, discontinue patient from study treatment.
Grade 4	Discontinue study treatment.	Discontinue study treatment.
Platelet count decreased (Thrombocytopenia)		
Grade 1 (PLT < LLN - 75 x 10 ⁹ /L)	Omit dose of cisplatin until resolved to CTCAE Grade ≤ 1, then maintain dose level	Omit dose of carboplatin until resolved to CTCAE Grade ≤ 1, then maintain dose level
Grade 2 (PLT < 75 - 50 x 10 ⁹ /L)	Omit dose of cisplatin until resolved to CTCAE Grade ≤ 1, then ↓ 1 dose level	Omit dose of carboplatin until resolved to CTCAE Grade ≤ 1, then ↓ 1 dose level
Grade 3 (PLT < 50 - 25 x 10 ⁹ /L)	Omit dose of cisplatin until resolved	Omit dose of carboplatin until

Worst Toxicity CTCAE v4.0 Grade (unless otherwise specified)	Recommended Dose Modifications to cisplatin any time during a cycle of therapy	Recommended Dose Modifications to carboplatin any time during a cycle of therapy
	to CTCAE Grade \leq 1, then - If resolved in \leq 7 days, then then ↓ 1 dose level. - If resolved in $>$ 7 days, then discontinue study treatment.	resolved to CTCAE Grade \leq 1, then - If resolved in \leq 7 days, then then ↓ 1 dose level. - If resolved in $>$ 7 days, then discontinue study treatment.
Grade 4 (PLT $<$ 25 x 10 ⁹ /L)	Discontinue study treatment.	Discontinue study treatment
Bleeding		
Any bleeding (related to cisplatin or carboplatin) resulting in a transfusion requirement	Omit dose of cisplatin until no further bleeding has been observed. Continuation of study treatment may be considered.	Omit dose of carboplatin until no further bleeding has been observed. Continuation of study treatment may be considered.
INVESTIGATIONS – RENAL		
Serum creatinine		
Grade 1 ($>$ ULN - 1.5 x ULN)	Maintain dose level.	Maintain dose level
Grade 2 ($>$ 1.5 - 3.0 x ULN)	Omit dose of cisplatin until resolved to CTCAE Grade \leq 1 or baseline, then - If resolved in \leq 7 days, then maintain dose level. - If resolved in $>$ 7 days, then ↓ 1 dose level.	Omit dose of carboplatin until resolved to CTCAE Grade \leq 1 or baseline, then - If resolved in \leq 7 days, then maintain dose level. - If resolved in $>$ 7 days, then ↓ 1 dose level.
Grade \geq 3 ($>$ 3.0 x ULN)	Discontinue study treatment.	Discontinue study treatment
INVESTIGATIONS – HEPATIC		
Blood Bilirubin ^b (for patients with Gilbert Syndrome these dose modifications apply to changes in direct bilirubin only) For patients with total bilirubin \geq grade 3, a CT scan or equivalent imaging procedure to exclude disease progression or potential other liver disease should be performed.		
Grade 1 ($>$ ULN – 1.5 x ULN)	Maintain dose level.	Maintain dose level
Grade 2 ($>$ 1.5 – 3.0 x ULN)	Omit dose of cisplatin until resolved to CTCAE Grade \leq 1, then - If resolved in \leq 7 days, then maintain dose level. - If resolved in $>$ 7 days, then ↓ 1 dose level.	Omit dose of carboplatin until resolved to CTCAE Grade \leq 1, then - If resolved in \leq 7 days, then maintain dose level. - If resolved in $>$ 7 days, then ↓ 1 dose level.
Grade 3 ($>$ 3.0 – 10 x ULN) or higher	Discontinue study treatment. NOTE: If CTCAE Grade 3 or 4 hyper-bilirubinemia is due to the indirect (non-conjugated) component only, and hemolysis as the etiology has been ruled out as per institutional guidelines (e.g. review of peripheral blood smear and haptoglobin determination), then ↓ 1 dose level and continue treatment at the discretion of the Investigator.	Discontinue study treatment. NOTE: If Grade 3 or Grade 4 hyperbilirubinemia is due to the indirect (unconjugated) component only, and hemolysis as the etiology has been ruled out as per institutional guidelines (e.g., review of peripheral blood smear and haptoglobin determination), then ↓ 1 dose level and continue treatment at the discretion of the investigator.
AST or ALT		

Worst Toxicity CTCAE v4.0 Grade (unless otherwise specified)	Recommended Dose Modifications to cisplatin any time during a cycle of therapy	Recommended Dose Modifications to carboplatin any time during a cycle of therapy
Grade 1 and 2 (up to 5.0 x ULN)	Maintain dose level.	Maintain dose level.
Grade 3 (> 5.0 - 20.0 x ULN)	Omit dose of cisplatin until resolved to CTCAE Grade ≤ 1, then 
 - If resolved in ≤ 7 days, then maintain dose level. - If resolved in > 7 days, then ↓ 1 dose level. 	Omit dose of carboplatin until resolved to Grade ≤1, then 
 - If resolved in ≤ 7 days, then maintain dose level - If resolved in > 7 days, then ↓ 1 dose level
Grade 4 (> 20.0 x ULN)	Discontinue study treatment.	Discontinue study treatment
NERVOUS SYSTEM DISORDERS		
Neurotoxicity		
Grade 1	Maintain dose level.	Maintain dose level.
Transient Grade 2 that improves to grade 1 on the day of planned therapy	Maintain dose level.	Maintain dose level.
Grade 2	Omit dose of cisplatin until resolved to CTCAE Grade ≤ 1, then ↓ 1 dose level.	Omit dose of carboplatin until resolved to CTCAE Grade ≤ 1, then ↓ 1 dose level.
Grade ≥ 3 or second occurrence of Grade 2	Discontinue study treatment.	Discontinue study treatment.
GI DISORDERS		
Diarrhea		
Grade 1	Maintain dose level, but initiate anti-diarrhea treatment as clinically indicated	Maintain dose level, but initiate anti-diarrhea treatment as clinically indicated
Grade 2	Omit dose of cisplatin until resolved to CTCAE Grade ≤ 1, including with appropriate management, then maintain dose level.	Omit dose of carboplatin until resolved to CTCAE Grade ≤ 1, including with appropriate management, then maintain dose level.
Grade 3	Omit dose of cisplatin until resolved to CTCAE Grade ≤ 1, initiate anti-diarrhea treatment, then 
 - If resolved in ≤ 48 hours, maintain dose level. - If resolved in > 48 hours, then ↓ 1 dose level. For 2nd occurrence of diarrhea CTCAE Grade 3 for > 48 hours despite the use of anti-diarrhea treatment, discontinue study treatment.	Omit dose of carboplatin until resolved to CTCAE Grade ≤ 1, initiate anti-diarrhea treatment, then 
 - If resolved in ≤ 48 hours, maintain dose level. - If resolved in > 48 hours, then ↓ 1 dose level. For 2nd occurrence of diarrhea CTCAE Grade 3 for > 48 hours despite the use of anti-diarrhea treatment, discontinue study treatment.
Grade 4	Discontinue study treatment.	Discontinue study treatment.
Nausea/Vomiting		
Grade 1	Maintain dose level, but initiate anti-emetic treatment.	Maintain dose level, but initiate anti-emetic treatment.
Transient Grade 2 that improves to grade 1 on the day of planned therapy	Maintain dose level.	Maintain dose level.

Worst Toxicity CTCAE v4.0 Grade (unless otherwise specified)	Recommended Dose Modifications to cisplatin any time during a cycle of therapy	Recommended Dose Modifications to carboplatin any time during a cycle of therapy
Grade 2	Omit dose of cisplatin until resolved to CTCAE Grade ≤ 1, initiate anti-emetic treatment, then maintain dose level.	Omit dose of carboplatin until resolved to CTCAE Grade ≤ 1, initiate anti-emetic treatment, then maintain dose level.
Grade 3	Omit dose of cisplatin until resolved to CTCAE Grade ≤ 1, initiate anti-emetic treatment, then: - If resolved in ≤ 48 hours, maintain dose level. - If resolved in > 48 hours, then ↓ 1 dose level.	Omit dose of carboplatin until resolved to CTCAE Grade ≤ 1, initiate anti-emetic treatment, then: - If resolved in ≤ 48 hours, maintain dose level. - If resolved in > 48 hours, then ↓ 1 dose level.
Grade 4	Discontinue study treatment.	Discontinue study treatment.
GENERAL DISORDERS		
Fatigue		
Grade 1 or 2	Maintain dose level.	Maintain dose level.
Grade 3	Omit dose of cisplatin until resolved to CTCAE Grade ≤ 1, then - If resolved in ≤ 7 days, maintain dose level. - If resolved in > 7 days, discontinue patient from study treatment.	Omit dose of carboplatin until resolved to CTCAE Grade ≤ 1, then - If resolved in ≤ 7 days, maintain dose level. - If resolved in > 7 days, discontinue patient from study treatment.
Grade 4	Discontinue study treatment.	Discontinue study treatment.
INFUSION REACTIONS		
Infusion reactions		
Grade 1 (Transient flushing or rash, fever < 38 °C [$<100.4^{\circ}\text{F}$]; intervention not indicated)	
 - Stop infusion - Treat per institutional guidelines. - May resume infusion (within 4 hours of initial start of infusion) at 50% of previous under continuous observation. Ensure that there is a minimum observation period of 1 hour prior to restarting the infusion. - Maintain dose level. - If the AE recurs at the reinitiated slow rate of infusion, and despite oral pre-medication, then do not resume infusion. 	
 - Stop infusion - Treat per institutional guidelines. - May resume infusion (within 4 hours of initial start of infusion) at 50% of previous under continuous observation. Ensure that there is a minimum observation period of 1 hour prior to restarting the infusion. - Maintain dose level. - If the AE recurs at the reinitiated slow rate of infusion, and despite oral pre-medication, then do not resume infusion.
Grade 2 (Intervention or infusion interruption indicated; responds promptly to symptomatic treatment [e.g., antihistamines, NSAIDS, narcotics]; prophylactic medications indicated for ≤24 hrs)	
 - Stop infusion - Treat per institutional guidelines. - May resume infusion (within 4 hours of initial start of infusion) at 50% of previous under continuous observation. Ensure that there is a minimum observation period of 1 hour prior to restarting the infusion. - Maintain dose level. - If the AE recurs at the reinitiated slow rate of infusion, and despite oral pre-medication, then do not 	
 - Stop infusion - Treat per institutional guidelines. - May resume infusion (within 4 hours of initial start of infusion) at 50% of previous under continuous observation. Ensure that there is a minimum observation period of 1 hour prior to restarting the infusion. - Maintain dose level. - If the AE recurs at the reinitiated slow rate of infusion, and despite oral pre-medication, then do not

Worst Toxicity CTCAE v4.0 Grade (unless otherwise specified)	Recommended Dose Modifications to cisplatin any time during a cycle of therapy	Recommended Dose Modifications to carboplatin any time during a cycle of therapy
	resume infusion.	resume infusion.
Grade 3 Prolonged [e.g., not rapidly responsive to symptomatic medication and/or brief interruption of infusion]; recurrence of symptoms following initial improvement; hospitalization indicated for clinical sequelae [e.g., renal impairment, pulmonary infiltrates])	
 - Discontinue infusion immediately - Treat per institutional guidelines. - Discontinue patient from study. 	
 - Discontinue infusion immediately - Treat per institutional guidelines. - Discontinue patient from study.
Grade 4 (Life-threatening; urgent intervention indicated)	
 - Discontinue infusion immediately - Treat per institutional guidelines. - Discontinue patient from study. 	
 - Discontinue infusion immediately - Treat per institutional guidelines. - Discontinue patient from study.
OTHER ADVERSE EVENTS		
Grade 1 or 2	Maintain dose level of cisplatin or carboplatin. For intolerable grade 2 toxicity, may omit dose of cisplatin or carboplatin until resolved.	
Grade 3	Omit dose of cisplatin or carboplatin until resolved to CTCAE Grade \leq 1, then \downarrow dose level of cisplatin or carboplatin.	
Grade 4	Discontinue study treatment.	

NOTE: All of the above are general guidelines. The investigator may omit dose of drug, decrease dose level of drug, or remove any patient from study for any toxicity, if he/she believes that it is in the best interest of the patient.
 
If a patient requires a dose delay of > 21 consecutive days of cisplatin or carboplatin then the patient must be discontinued from the study treatment. Patients who discontinue from the study for a study-related adverse event or an abnormal laboratory value must be followed at least once a week for 3 weeks and subsequently at 3-week intervals, until resolution or stabilization of the event, whichever comes first, unless stated otherwise.
		

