5.3.4 Cisplatin or Carboplatin Dose Modifications

- **Dose reductions:** For non-hematologic grade 3 and 4 AEs (except for nausea and vomiting as well as AEs unrelated to treatment) the dose should be reduced according to the Cisplatin/Carboplatin Dose Level Table at the discretion of the investigator. Dose reductions for treatment day (or within 2 days of treatment) ANC and platelet counts should also be made according to the Dose Level Table below.

NOTE: The etoposide will be held if platinum is held until a decision is made to skip platinum for the current cycle so that all drugs are kept on the same schedule.

- **Discontinuation** Also, except for nausea and vomiting, if any of the same non-hematologic grade 3 and 4 AEs that are at least possibly related to platinum recur after two reductions for that AE, then platinum will be stopped.
- A patient's protocol treatment will be discontinued if more than 2 cumulative dose reductions are necessary or if patients are unable to restart platinum within 3 weeks of interruption. Dose reductions will be permanent. Missed doses will be made up once toxicity is resolved per guidelines below.
- All toxicity grades below are described using the NCI Common Terminology Criteria for Adverse Events (CTCAE) version 4.0.

Cisplatin Dose Level Table	
Dose Level	Dose in mg/m ² (days 1-3)
0	25
-1	20
-2	16

*Note this is a 20% dose reduction with each dose level.

Carboplatin Dose Level Table	
Dose Level	Dose in AUC (day 1)
0	5
-1	4

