5.3.5.1 Hematologic Toxicity

ANC (/mm ³)		Platelets (/mm ³)	Modification
< 1500/mm ³	and/or	< 100,000/mm ³	Hold until ANC \geq 1500/mm ³ and platelets are \geq 100,000/mm ³ , resume at 20% dose reduction*
\geq 1500/mm ³	and	\geq 100,000/mm ³	No dose modification

*This table applies to day of treatment (or within 2 days of treatment) hematologic toxicities.

*If ANC and platelet count recover within one week, resume therapy at 100%. If greater than 7 days to recovery, upon recovery to ANC \geq 1,500/mm³ and platelets to \geq 100,000/mm³, the dose level -1 will be administered (80 mg/m²). Discontinue etoposide dose if patients do not recover within \leq 3 weeks. If patient was already receiving Etoposide at the -1 dose level, reduce to the -2 dose (64 mg/m²).

If already receiving treatment at the -1 dose level, upon recovery to ANC \geq 1,500/mm³ and platelets to \geq 100,000/mm³, the dose level -2 will be administered (64 mg/m²). Discontinue dose if patients do not recover within \leq 3 weeks. If patient was already receiving Etoposide at the -2 dose level, treatment should be discontinued.

Neutropenia or Febrile Neutropenia

For nadir neutropenia in the absence of fever or with fever that is successfully treated by oral antibiotics, there will be no dose adjustment. Filgrastim, sargramostim, or pegfilgrastim are allowed and should be administered according to ASCO guidelines (54). For treatment delays due to chemotherapy toxicities of more than 7 days, Etoposide should be dose-reduced according to the Etoposide Dose Level Table for all subsequent cycles of chemotherapy. For neutropenic fever (ANC < 500/mm³) and temperature $>$ 100.5F) requiring intravenous antibiotics, the doses of all chemotherapy drugs (cisplatin and etoposide) should be reduced by one dose level according to the Etoposide Dose Level Table and the Cisplatin Dose Level Table for the next cycle and all subsequent cycles. If counts to not recover within 4 weeks, discontinue all protocol therapy.

Thrombocytopenia

For grade 4 nadir platelet count decrease (thrombocytopenia) (platelets < 25,000/mm³), the dose of Etoposide should be reduced by one dose level according to the Etoposide Dose Level Table for the next cycle and for all subsequent cycles of chemotherapy. If counts do not recover within 4 weeks, discontinue all protocol therapy.

Anemia

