5.3.5.2 Non-hematologic Toxicity

Gastrointestinal Toxicity, Nausea and Vomiting

All patients should receive antiemetics* to prevent nausea and vomiting. Steroids and 5-HT3 antagonists are required premedications but additional specific antiemetic therapy is left to the discretion of the treatment physician. If vomiting is severe, consider hospital admission and/or use of aprepitant if possible. Do not modify chemotherapy doses.

*Aprepitant, when given once daily for 14 days as a 100 mg capsule with an oral contraceptive containing 35 mcg of ethinyl estradiol and 1 mg of norethindrone, decreased the AUC of ethinyl estradiol by 43% and decreased the AUC of norethindrone by 8%. Women of childbearing potential using pregnancy contraception that includes ethinyl estradiol should not receive Aprepitant for the treatment of nausea/delayed emesis. Patients may change to a different method of contraception if they wish to use Aprepitant.

Hepatotoxicity

Bilirubin	Etoposide*
≤ 1.5 X ULN	100%
> 1.5 – 3.0 X ULN	50%
> 3.0 X - ≤ 5.0 ULN	30%
> 5 X ULN	Hold**

* Please note that the % dose administered is based on the original starting dose of etoposide (100 mg/m²). If patient is at dose level -1 or -2, % should be based on reduced dose the patient is currently on, not original dose.

** For bilirubin greater than 5 X ULN it is recommended not to use etoposide for that cycle but this is at the discretion of the treating physician. If holding, repeat labs on a weekly basis for

up to 3 weeks until total bilirubin is \leq 5 X ULN. The cisplatin dose should also be held if etoposide is held so that all drugs are kept on the same schedule. If bilirubin improves within 3 weeks to \leq 5 X ULN, then resume treatment and use reduced dose per table above. If bilirubin does not improve to \leq 5 X ULN within 4 weeks, discontinue protocol therapy.

Hypomagnesemia

Hypomagnesemia is not an indication for stopping therapy. Oral or parenteral magnesium supplementation is indicated for serum magnesium levels $<$ 1.5 mEq/L.

Allergic Reactions

Discontinue all protocol treatment promptly if \geq grade 3 anaphylaxis develops.

Suggested Management of Allergic Reaction:

In case of mild allergic symptoms (e.g., appearance of a localized or generalized pruritus), symptomatic treatment may be given (e.g., oral antihistamine or corticosteroids).

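### At treatment-day platelets of 75,000–99,999/mm³ or ANC of 1,000–1,499/mm³, etoposide is held but no working rule holds the platinum

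*Combined protocol and SAP*

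**What the plan says.** Three sets of rules in the protocol bear on an Arm B treatment day.

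- **Etoposide (5.3.5.1).** Hold if ANC is below 1,500/mm³ and/or platelets are below 100,000/mm³, until both have recovered. On timing: "This table applies to day of treatment (or within 2 days of treatment) hematologic toxicities".
- **Platinum (5.3.4.1).** The cisplatin column is headed "Recommended Dose Modifications to cisplatin any time during a cycle of therapy", and the carboplatin column likewise, so treatment days are included. For Grade 1 platelets (below LLN down to 75 × 10⁹/L) the cisplatin entry is "Omit dose of cisplatin until resolved to CTCAE Grade ≤ 1, then maintain dose level", and the carboplatin entry is the same apart from the drug name. The ANC row beginning "Grade 2 (ANC < 1.5 - 1.0 x 10" keeps the dose level for both agents.
- **Links between the drugs.** The note in 5.3.4 says "The etoposide will be held if platinum is held until a decision is made to skip platinum for the current cycle", so that the drugs stay on one schedule. In 5.3.5.2, within the footnote on bilirubin above 5 × ULN, the reverse appears: "The cisplatin dose should also be held if etoposide is held so that all drugs are kept on the same schedule".

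**The concern.** A hold that ends at Grade 1 or better cannot act on a patient who is at Grade 1. Separately, etoposide and platinum have different count thresholds, and the only general link runs from platinum to etoposide. Taken literally, the rules let a site give platinum on its due day while etoposide waits.

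That splits a doublet which both linking notes want kept on one schedule. It also leaves sites with an unclear safety instruction for marrow-suppressive drugs. Section 7.1 requires a CBC before each cycle, so the question can arise at every cycle. What is at stake is consistent delivery of the control regimen, not the size of the trial or its primary test.

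**Working it through.** The plan gives no figure to reproduce here. The check sets the rules side by side for each count band and asks whether each platinum hold is still in force once it starts. Units are aligned first: 75 × 10⁹/L = 75,000/mm³, and 1.0–1.5 × 10⁹/L = 1,000–1,500/mm³.

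| Treatment-day count (/mm³) | Etoposide, 5.3.5.1 | Platinum, 5.3.4.1 | Platinum held? |
|---|---|---|---|
| Platelets 75,000–99,999 (Grade 1) | Hold | Omit until Grade ≤ 1, already met; same dose | No |
| Platelets below 75,000 (Grade 2 or worse) | Hold | Omit until Grade ≤ 1, or discontinue | Yes, up to 75,000 |
| Platelets back at 75,000–99,999 after Grade 2 or 3 | Hold | Released one dose level lower (after Grade 3, only if resolved within 7 days) | No |
| ANC 1,000–1,499 (Grade 2) | Hold | Dose level kept, no hold stated | No |
| ANC below 1,000 (Grade 3–4) | Hold | Omit until Grade ≤ 1, which is 1,500 | Yes, same restart point as etoposide |

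**Size of the bands.** Platelets: 100,000 − 75,000 = 25,000/mm³, reached in three situations (Grade 1, recovery from Grade 2, recovery from Grade 3). ANC: 1,500 − 1,000 = 500/mm³, in one situation (Grade 2, not on the way back from Grade 3–4).

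**Is the Grade 1 platelet row an anomaly?** Outside infusion reactions, 5.3.4.1 has 10 other Grade 1 entries: anemia, ANC, creatinine, bilirubin, AST/ALT, neurotoxicity, diarrhea, nausea/vomiting, fatigue and other adverse events. All 10 keep the dose level. The release point in the Grade 1 platelet row is the one used in the Grade 2 row below it, where it does work.

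**Does another rule close the gap?**

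- 5.3.4 mentions treatment-day counts, but for dose reductions; it sets no count at which platinum is held.
- The 5.3.4 note starts from a platinum hold, so it does not apply when only etoposide is held.
- The 5.3.5.2 sentence belongs to the bilirubin footnote. Even read as a general rule, it leaves out carboplatin, which 5.1.2 allows at the physician's choice.
- 5.3.5.2 also stops all therapy for other Grade 3–4 toxicity, but only non-hematologic toxicity.
- Sections 5.1.2, 5.3.1, 8.3 and 8.4 give no further treatment-day count threshold for platinum.

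None of these holds platinum in either band. Correcting the platelet row alone would leave the ANC band open.

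**The case against.** The strongest reply is that the maintain-dose instruction in 5.3.4.1 sets the dose, not the timing, since the same words also follow holds. On that reading the Grade 2 ANC row is silent on delay, and there are not two conflicting orders. This is fair, but silence still leaves platinum with no hold on the day it is due.

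Next, a site could read the Grade 1 platelet row as a real hold with a mistyped release point. The 5.3.4 note would then keep etoposide with it. That reading is possible, but it gives a hold with no defined end and does nothing for ANC.

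The evidence on intent is mixed. Section 5.3.1 allows one agent to be stopped and the other continued only in Arm A, but it concerns discontinuation, not a temporary hold. The 5.3.4 note itself contemplates skipping platinum for a cycle. So 5.3.1 is only supporting evidence. The firmer ground is the same-schedule aim stated in both linking notes.

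Finally, 5.3.4.1 describes its contents as general guidelines and lets the investigator omit any dose, so holding both drugs is already allowed, and many investigators would probably do so. This limits the consequence. It does not tell sites which action is intended.

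**Conclusion.** The point holds. In the two bands, etoposide is held and no working rule holds cisplatin or carboplatin; the hold in the Grade 1 platelet row is void as written. The cause is different thresholds combined with a one-way link, not the platelet row alone.

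Labelling the whole 75,000–99,999/mm³ band Grade 1 assumes an LLN of at least 100,000/mm³. With a lower LLN, counts between it and 100,000/mm³ would fall in no platinum row, and the gap would remain.

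Frequency cannot be calculated from the documents. The platelet band is plausible with carboplatin: 8.4.11.1 puts the nadir at about day 21 and recovery by day 28–30, against 21-day cycles. The rule should be corrected because it is a safety instruction that fails as written. Sample size and the PFS analysis do not change.

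**What to change.** Two changes in the next amendment:

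1. In 5.3.4.1, replace the Grade 1 platelet entry for both agents with *Maintain dose level.*
2. Add to 5.3.4 and 5.3.5.1: *If etoposide is held for ANC or platelets on the treatment day (or within 2 days of it), hold cisplatin or carboplatin as well until etoposide can restart (ANC ≥ 1,500/mm³ and platelets ≥ 100,000/mm³), so that both drugs stay on the same schedule. The platinum dose at restart follows 5.3.4.1.*

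The first change sets the dose and the second sets the timing, so they do not conflict. The Grade 2 and 3 platelet rows need no separate restart threshold, and the 7-day clock in the Grade 3 row stays on Grade ≤ 1.

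The drafting cost is one table row and one sentence in two places. The clinical cost is that some platinum doses are delayed. That time counts toward the 5.3.4 limit ("if patients are unable to restart platinum within 3 weeks of interruption") and the 21-day limit in 5.3.4.1. A patient whose counts stay in either band for more than 3 weeks would leave protocol treatment. Section 5.3.5.1 already stops etoposide at that point ("Discontinue etoposide dose if patients do not recover within" 3 weeks), so the added loss is platinum alone. This downside looks small, but its frequency is as unknown as that of the gap. No sample-size or analysis change is needed.
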